5.10 Statistical methods and data analysis

Data endpoints for quantitative analyses and the means of calculating the proportions are summarised in table 1. For objectives 2 and 3 endpoints will be compared between Truenat and standard of care.

Cleaning and analysis of quantitative data will be conducted using R (The R Project for Statistical Computing, v4.1.2). QSR nVIVO will be used to support the coding and analysis of qualitative data.

5.10.1 Objective 1

Objective 1a

Proficiency in performing testing using Truenat Mtb Plus and MTB-RIF Dx will be assessed for all persons who undertake the training. The proportion of users who were proficient in their first post-training test will be calculated. Score summaries will be analysed as descriptive data. Among those who did not pass their first post-training, proportions will be calculated for failure for each of the competencies in the checklist. The median number and range for the number of repeat tests until proficient will be calculated for those who fail their first test.

Objective 1b

Descriptive statistics will be calculated for the number and proportion of hours that the platform was unavailable due to failure, with further disaggregation of failure by the reason for the failure. Descriptive statistics will also be calculated for the proportion of assays with an error, with disaggregation by error type.

Objective 1c

Survey data from closed-ended user feasibility and acceptability survey questions will be analysed to produce contingency tables and plots of the data, while open-ended survey questions will be coded and analysed qualitatively using a thematic approach.

Objective 1d

Patient in-depth semi-structured interviews will be analysed thematically: transcripts will be translated from Indonesian and coded using previously identified thematic codes from survey and interview guide development as well as codes that emerge during analysis. All coding will be done by at least two researchers, aiming for independent review followed by consensus through

LOCATE TB Research Protocol v1.1 (2022-08-25)

discussion. Themes and findings will be analysed both separately (users, HCWs and patients) and combined as a means of cross verification. QSR NVivo will be used to support the coding and analysis of qualitative data.

5.10.2 Objectives 2 and 3:

For study participants who are tested using a TB molecular diagnostic test, the median time from sample collection to result will be calculated and a test of significance will be performed on the medians from the standard of care group and the Truenat group. The expected number of patients diagnosed with bacteriologically confirmed TB is expected to be too small to give sufficient power to detect a difference in median time to treatment start in these patients. Nonetheless, the median time from sample collection to treatment initiation will be calculated for the two groups. Time to event analyses will be described by Kaplan-Meier-curves by diagnostic arm. Details will be presented in the Statistical Analysis Plan.

Interquartile ranges (IQRs) and box and whisker plots will be generated for all medians, with differences in medians compared using the Wilcoxon signed rank test (Mann-Whitney *U*). Interim data analysis will occur at the study mid-point, with results reviewed by the study team.

Endpoint	Numerator	Denominator	Data source
Objective 1	 		 
Proportion of	Staff trained	All staff trained	Post training assessment
staff trained who	achieving		
were deemed	proficiency in post		
proficient	training assessment		
Proportion of	Number of Truenat	Number of	Mobile ACF service error
tests performed	tests with error or	Truenat tests	form
with an error	invalid result	performed	
Proportion of	Time (hours and	Time (hours and	Mobile ACF service
time of device	minutes) of device	minutes) during	laboratory availability
unavailability for	unavailability during	screening days	records
use during	Truenat screening	when Truenat	

TABLE 1: ENDPOINTS AND DATA SOURCES

working day	days for any reason	randomized to be	
		available	
Objectives 2 and 3			
Madian tinga ta		Γ	Activo caso finding
Median time to			Active case midning
diagnostic test result			database (Redcap)
for participants			Laboratory database
tested with a TB			
molecular diagnostic			
test			
Median time to			Active case finding
treatment			database
initiation for			Deeleenee Deteleen
participants with			Pusksemas Database
an initial positive			Week-1 telephone call
result on a TB			
molecular			
diagnostic test			

Mixed-Methods Analysis and Outputs

For the feasibility and acceptability assessment a mixed methods framework will be used. Each component of the study will initially be analysed individually in parallel. The mixed methods analysis will use the triangulation framework described by Erzberger and Kelle. (Tashakkori & Teddlie, 2010) This will facilitate a discussion of the relationships between the qualitative and quantitative data sets and the theoretical concepts underpinning the study. The theoretical framework is highlighted in the diagram below.

Proposition: Decentralised Truenat MTB Plus and MTB-RIF Dx is well accepted by laboratory and non-laboratory staff as well as community members and is operationally feasible being easy to use with high proficiency and with low

The combination of the quantitative and qualitative analyses allows triangulation of the data with the theoretical proposition thereby strengthening the overall analysis and interpretation. Triangulation is a process of using different methods to study a problem, thereby achieving a deeper exploration of observations and perceptions to build a more complete picture than each method would be able to provide individually. (O'Cathain, Murphy, & Nicholl, 2010) Through this process an exploration can be undertaken to look for: convergent findings which are similar findings between the qualitative and quantitative aspects or divergent findings where for example users might report ease of use, however be observed to have difficulty with certain aspects of the test. The results from the different feasibility and acceptability analyses will be synthesised giving equal weighting to each type of analysis. The investigators will review the findings from the analyses and discuss as a team to seek to understand the potential logical relationships between the observed data, the interview findings and the theoretical proposition.

6 Ethics and community engagement

6.1 **Basic Principles**

The study will be performed in accordance with the study protocol, national regulations, and the ICH-Harmonised Tripartite Guideline for GCP E6 (R1) (1996).

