3.2 Current Active Case Finding (Standard of Care)

Active TB case finding is community-based and utilises mobile chest X-ray units deployed in vans. Screening sites are chosen based on identification of potential 'hotspots' through mapping of reported cases over the past 3 years. Prior to a mobile screening event, the local health authorities and community leaders are consulted and information is disseminated to the community to invite those living close in potential 'hotspots' to attend a free TB screening, with information given of what is provided and where to attend. The mobile van teams conduct screening with COVID-19 safe precautions and can screen 80-120 people per day. Each person attending is screened using a symptom checklist to check for: cough for more than 2 weeks; fever; night sweats; weight loss/failure to thrive; and haemoptysis. In addition, all persons over the age of 5 receive a chest Xray (CXR) on the van. The CXR is read by qXR, a computer aided detection software. Persons may screen positive based on either their reported symptoms or their CXR, which are suggestive of TB. Spot sputum sample collection is attempted from all individuals who screen positive. Samples are then transported as a batch to a central laboratory for GeneXpert testing.

LOCATE TB Research Protocol v1.1 (2022-08-25)

Additionally, active case finding services include screening of household contacts. Newly registered TB cases are visited, and household members are screened for symptoms; for latent TB infection with a tuberculin skin test if eligible; and referred for a CXR at the mobile van services or nearest CXR facility.

Referral of sputum specimens centrally leads to delays in diagnosis and required extra visits from healthcare workers to follow up and contact patients with TB. Provision of TB molecular testing capacity within the mobile screening service could reduce diagnostic delays, reduce diagnostic loss to follow up and increase community acceptability.

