5.1 Study Design

This is a prospective mixed-methods implementation science study to evaluate the use of Truenat MTB Plus and MTB-RIF Dx (Truenat) within a mobile active case finding service. Specific methods will be used for each of the endpoints under the primary objective.

For the **primary objective**, operational performance will be assessed through laboratory staff and health care worker Truenat proficiency assessments after initial training (1a), and measurement of platform error rates during the study (1b). Views on the acceptability and operational challenges of Truenat will be assessed by a survey of laboratory staff and health care workers (HCW) within the program (1c). Individual in-depth qualitative interviews will be conducted with a purposive sample of screening participants to obtain their views on the acceptability and suitability of decentralised testing using Truenat (1d). The purposive sampling of screening participants will deliberately target the inclusion of participants representing a diversity of sex, age, microbiological positivity, and risk populations.

For the **secondary objectives**, a randomised comparison of decentralised microbiological testing using Truenat Mtb Plus and MTB-RIF Dx compared with standard of care centralised GeneXpert testing will be conducted. Screening days will be randomised 1:1 to the Truenat or standard of care, and the participants screened on those days then being assigned to corresponding study arm (Truenat arm or standard of care arm). Randomisation will be done across screening days within 2-week blocks for case finding activities. Only management staff will be informed in advance of the assignment for screening days to organise staff schedules. Community mobilisation will be done by the community cadre who will not know which screening type is being performed on any specific day, to reduce the potential for people in the community preferentially choosing a screening day based on which test will be available.

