The mobile service screens 1000 people per month with 12.1% of participants in rural areas screening positive and requiring microbiological examination of sputum samples. We will enrol participants for a minimum of 6 months and a maximum of 9. Which would result in between 3000–4500 persons screened in each arm. Consequently, per the calculations below, the sample will be sufficiently powered to detect a difference in median time to result of one or more days with an alpha of 0.05 and power of 0.8. This would require a minimum of 211 microbiological examinations in each arm. Throughput in of 3000–4500 persons would be expected to result in 363–544 microbiological examinations in each arm.

Median time to result standard of care	Median time to result Truenat	Alpha	Power	Sample size per arm
3 (sd = 14)	1 (sd = 14)	0.05	0.8	29
3 (sd = 21)	1 (sd = 21)	0.05	0.8	34
3 (sd = 14)	2 (sd = 14)	0.05	0.8	175
3 (sd = 21)	2 (sd = 21)	0.05	0.8	211

These assumptions are based on the current active case finding TB diagnostic cascade from the PRIME-TB/TB REACH project in Yogyakarta in 2020 and 2021, which includes the impact of COVID-19 on activities.

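### Whole screening days are randomised but the named test for time to result treats participants as independent, so its type I error exceeds 0.05 by an amount that depends on an unstated within-day correlation

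*Protocol*

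**What the plan says.** Section 5.1 of the protocol sets the unit of allocation: "Screening days will be randomised 1:1 to the Truenat or standard of care". It adds that "Randomisation will be done across screening days within 2-week blocks". Participants screened on a day are assigned to that day's arm.

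Section 5.10.2 fixes the comparison of time from sample collection to result: "a test of significance will be performed on the medians from the standard of care group and the Truenat group". The next paragraph has "differences in medians compared using the Wilcoxon signed rank test", with Mann-Whitney U in brackets. The arms are separate groups of people, so the two-sample Mann-Whitney test must be the one meant. No term for day or block is mentioned. The section also says "Details will be presented in the Statistical Analysis Plan".

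Section 5.9.2 plans to detect a difference in median time to result of "one or more days with an alpha of 0.05 and power of 0.8", and concludes: "This would require a minimum of 211 microbiological examinations in each arm". It mentions no ICC or design effect.

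Section 3.2 describes the standard-of-care pathway: "Samples are then transported as a batch to a central laboratory for GeneXpert testing".

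**The concern.** A Mann-Whitney test on participants takes its reference distribution from independent observations. Here the independent units are days. Anything that speeds or slows a whole day's results moves all of that day's participants together, and all of them are in one arm. Batch transport is such a factor: a late courier or a laboratory backlog delays the whole batch. The Truenat arm has its own: section 5.4.1 (1b) provides for logging outages from device failure or battery depletion, which would hold up everyone still to be tested that day. Given such correlation, the arm difference varies more from one allocation to another than the test allows, and the p-value is too small.

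Time to result is the only randomised comparison for which the protocol claims adequate power. Section 5.10.2 concedes that time to treatment will be underpowered. Section 6.4 says that the study will directly inform government decisions on scaling up mobile screening, so the p-value should have the error rate used in planning.

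**Working it through.** **1. The plan's own figure.** The four sample sizes in 5.9.2 reproduce if times are lognormal and participants are individually randomised.

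- Log-scale variance from a median M and standard deviation SD: s² = ln{[1 + √(1 + 4(SD/M)²)]/2}
- Per arm: n = (s₁² + s₂²)(1.960 + 0.842)² / [ln(M₁/M₂)]²
- Last row (3 v 2 days, SD 21): s₁² = 2.017 and s₂² = 2.399, so n = 4.416 × 7.849 / 0.1644 = 210.8, which rounds up to 211.
- The other rows give 28.1, 33.1 and 174.96, hence 29, 34 and 175, as stated.

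The match is exact, two-sided, with a design effect of 1. The planning therefore assumes independent participants, as the test does.

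**2. Inputs for the error rate.**

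- Tested per day, m: 80 to 120 screened per day (3.2) × 12.1% screening positive (5.9.2) = 9.7 to 14.5, or 12.1 at 100 screened.
- Days: 1000 screened per month / 100 per day = 10 per month, so 60 to 90 over 6 to 9 months, or 30 to 45 per arm.
- Within-day ICC, ρ: not in the protocol. Assumed, and varied below.

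**3. Error rate with the blocks left out.** Design effect DE = 1 + (m − 1)ρ. Actual two-sided type I error of the nominal 0.05 test = 2[1 − Φ(1.96/√DE)].

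| ρ | DE (m = 12.1) | type I error | over m = 9.7 to 14.5 |
|---|---|---|---|
| 0.01 | 1.11 | 0.063 | 0.060–0.066 |
| 0.05 | 1.56 | 0.116 | 0.102–0.130 |
| 0.10 | 2.11 | 0.177 | 0.152–0.201 |

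A Mann-Whitney test simulated under no true difference (60 days, about 12 tested per day, lognormal times cut to whole days, 3,000 trials per setting) rejected in 0.051 at ρ = 0, and in 0.064, 0.114 and 0.175 at the three values above. With 88 days (2,000 trials) the figures at those three values were 0.064, 0.119 and 0.165, so longer enrolment does not remove the problem.

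**4. Allowing for the blocks.** Variation shared by a whole 2-week block is balanced between the arms. If a share b of the between-day variance lies between blocks, and arms and day sizes are balanced within blocks, DE is replaced by (1 − ρ) + mρ(1 − b). With b = 0.5 and m = 12.1:

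- ρ = 0.01: 0.990 + 0.0605 = 1.05, error 0.056 (simulated 0.054)
- ρ = 0.05: 0.950 + 0.3025 = 1.25, error 0.080 (simulated 0.083)
- ρ = 0.10: 0.900 + 0.605 = 1.51, error 0.110 (simulated 0.110)

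The simulation used blocks of four screening days, which is an assumption. Its standard error near 0.05 is √(0.05 × 0.95/3000) = 0.004, so 0.054 cannot be told apart from 0.05. The adjusted factor stays above 1 as long as m(1 − b) > 1. At m = 12.1 the inflation vanishes only if the blocks absorb more than 1 − 1/12.1 = 92% of the between-day variance.

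**The case against.** **No ICC is given.** A reader might infer that the error rate is well above 0.05. The protocol does not support that as a plain statement: at ICC 0.01 the rate is about 0.06, or close to 0.05 with blocking. Batch transport makes a larger ICC plausible, but that is inference. This stands, and the size must be stated conditionally.

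**The mechanism may sit mainly in one arm.** Truenat samples are tested on site on the same day (5.4.2). If only standard-of-care days were correlated, averaging the design effects of the two arms at m = 12.1 gives 0.083 at ICC 0.05 [DE = (1.555 + 1)/2 = 1.28] and 0.116 at 0.10 [DE = (2.11 + 1)/2 = 1.56]. This reduces the excess without removing it, and device outages could correlate Truenat days as well.

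**Twelve per day may be too many.** It applies a rural positivity rate to the van's daily capacity and assumes that everyone consents and produces sputum. With 6 per day (an assumption), the error is 0.080 at ICC 0.05 and 0.110 at 0.10. This too only reduces the excess.

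**The consequences are limited.** This is a secondary endpoint in a study whose primary objective is feasibility. Same-day testing is compared with results expected in 1 to 3 days, so a true null is unlikely, and a large difference would survive a correct test. That is fair. But the protocol chose to test, and claims power for differences as small as one day, where the stated precision matters.

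**The SAP may deal with it.** It could. But the protocol itself names the test, and deferring details does not withdraw it.

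**Intervals.** A reader might also infer that the reported confidence interval will be too narrow. Section 5.10.2 plans interquartile ranges and box plots, and no interval for the difference in medians. The point applies only if one is added.

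**Conclusion.** The point holds in conditional form. The allocation in 5.1 and the test named in 5.10.2 do not match, and the sample size rests on the same independence assumption. Positive within-day correlation that the blocks do not absorb puts the type I error above 0.05.

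How far above is not known from the protocol. With about 12 tested per day, an ICC of 0.05 or more would at least double the rate if the blocks absorb nothing. An even split of the between-day variance between and within blocks would bring it to about 0.08 at ICC 0.05. These figures rest on an assumed ICC, an assumed 100 screened per day and an assumed split of variance. The direction does not depend on their exact values.

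**What to change.** In 5.10.2, keep the Mann-Whitney statistic but take its p-value from re-randomising screening days within their 2-week blocks, following the actual allocation procedure. This is valid by design whatever the ICC. An equivalent day-level method would also serve, such as a clustered rank test or an analysis of day summaries with block as a factor. If an interval for the difference in medians is reported, obtain it from a bootstrap that resamples whole days within arm and block. Settle the method before the arms are compared, including at the planned mid-point analysis.

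The cost is a sentence or two in the protocol or SAP and a short R routine. The enrolment instrument already records study date and assigned strategy (5.8.3), so no new data are needed; the block follows from the date and the randomisation schedule. The p-value will probably be somewhat less favourable.

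### Screening days are randomised within 2-week blocks, but the between-arm test and the sample size treat participants as independent, and the test is named in two incompatible ways

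*Protocol*

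**What the plan says.** Protocol section 5.1: "Screening days will be randomised 1:1 to the Truenat or standard of care", and participants are assigned to the arm of the day on which they were screened. The allocation is blocked in time: "Randomisation will be done across screening days within 2-week blocks for case finding activities".

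Section 5.10.2 works on individuals: "For study participants who are tested using a TB molecular diagnostic test, the median time from sample collection to result will be calculated". The arms are then compared, "with differences in medians compared using the Wilcoxon signed rank test", with Mann-Whitney U following in brackets as if it were the same test. Further detail is left to the statistical analysis plan.

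Section 5.9.2 claims adequate power for a difference in median time to result of "one or more days with an alpha of 0.05 and power of 0.8". It adds: "This would require a minimum of 211 microbiological examinations in each arm". It expects 363–544 examinations per arm. The protocol mentions no clustering, intracluster correlation (ICC) or design effect.

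On the standard-of-care pathway, section 3.2 says: "Samples are then transported as a batch to a central laboratory for GeneXpert testing".

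**The concern.** The unit that was randomised is the screening day, and the unit that is tested is the participant. A rank-sum test on pooled participants takes its reference distribution from independent observations. If people screened on the same day tend to get their results together, the number of independent pieces of information lies nearer the number of days than the number of people.

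The protocol gives reason to expect this. Standard-of-care samples are moved in a batch, so a transport or laboratory delay would tend to affect many of one day's samples. In the Truenat arm, a device outage of the kind that section 5.4.1 plans to log would delay that day's tests together. Shocks of this kind are specific to a day, so balancing days within 2-week blocks does not remove them.

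This is the only randomised, formally tested comparison in the study, and section 6.4 expects the study to inform government decisions on scale-up. A chance difference between days could be reported as significant, and the power statement could be too favourable.

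The naming of the test is a separate fault. The signed rank test is for paired data and Mann-Whitney U is for two independent groups. The arms are different people. The Truenat arm also has paired Truenat and GeneXpert results (section 5.4.2), so the paired name could be taken to mean a different, non-randomised comparison.

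**Working it through.** **1. Reproducing the plan's sample size.** Inputs from section 5.9.2: medians 3 and 2 days, SD 21 in each arm, alpha 0.05, power 0.8. Assume log-normal times and a two-sided test.

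- Log-variance: s² = ln[(1 + √(1 + 4·SD²/median²))/2]. For median 3: ln[(1 + √197)/2] = 2.017. For median 2: ln[(1 + √442)/2] = 2.399.
- n per arm = (2.017 + 2.399) × (1.960 + 0.842)² / (ln 1.5)² = 4.416 × 7.849 / 0.1644 = 210.8, rounded up to 211.
- The other three rows give 28.1, 33.1 and 175.0, against the stated 29, 34 and 175.

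All four rows reproduce with individuals as the unit and a design effect of exactly 1.

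**2. Number and size of days.** Inputs: 1000 screened per month, 12.1% needing a test and 6–9 months (section 5.9.2); 80–120 screened per day (section 3.2).

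- Examinations per arm: 3000–4500 × 0.121 = 363–544.5, as stated.
- Days: 6000/120 = 50 up to 9000/80 = 112, so about 25–56 per arm.
- Tested per day: 80–120 × 0.121 = 9.7–14.5, with m = 12.1 in the middle.

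**3. Effect of ignoring the day.** The ICC is an assumption. With design effect DE = 1 + (m − 1) × ICC:

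- actual alpha of the unadjusted test = 2 × [1 − Φ(1.96/√DE)]
- required n per arm = 211 × DE
- power at n per arm = Φ(√(n/(210.8 × DE)) × 2.802 − 1.960)

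The formula for alpha was checked by simulating Mann-Whitney tests with no true difference: 60 days randomised in blocks of 4, on average 12.1 tested per day, log-normal times (median 3, SD 21) rounded up to whole days, 3000 trials per setting.

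| Day ICC | DE | Alpha, formula | Alpha, simulated | Alpha, simulated, half the correlation shared across the block | Required n per arm | Power at 363 / 544 |
|---|---|---|---|---|---|---|
| 0.01 | 1.11 | 0.063 | 0.062 | 0.056 | 235 | 0.94 / 0.99 |
| 0.05 | 1.56 | 0.116 | 0.118 | 0.084 | 329 | 0.84 / 0.95 |
| 0.10 | 2.11 | 0.177 | 0.178 | 0.107 | 446 | 0.72 / 0.87 |
| 0.30 | 4.33 | 0.346 | 0.351 | 0.235 | 914 | 0.42 / 0.58 |

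When all the correlation is shared across the block, the simulated alpha is about 0.05. With clustering in the standard-of-care arm only, a separate simulation gave 0.08, 0.12 and 0.24 at ICC 0.05, 0.10 and 0.30. A comparison of day-level summaries stayed at 0.04–0.06 throughout.

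**4. Smaller days.** If the 1000 per month were spread over 20 days (an assumption), about 6 would be tested per day. DE is then about 1.25 at ICC 0.05 and 1.51 at 0.10, and alpha is about 0.08 and 0.11.

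**5. ICC at which the power claim fails.** 80% power for 3 against 2 days with SD 21 holds while 211 × DE is no more than the expected n. At m = 12.1 the limits are (363/211 − 1)/11.1 = 0.065 and (544/211 − 1)/11.1 = 0.14.

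**The case against.** The strongest reply is that the documents give no ICC, so the size of the error is not established. That stands. A reader might infer that the false-positive rate is several times 0.05. Three times nominal needs a within-block day ICC of about 0.06–0.10 for 9.7–14.5 tested per day. That is plausible with batched samples, but no figure in the protocol supports it. Three further points pull the same way:

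- The 80–120 per day is given as what a team can screen, not as an average. The 12.1% is a rural rate, while one of the two sites is a city.
- The protocol does not say that there is one batch per day, or that a batch's results come back together.
- Correlation shared across a 2-week block is balanced by the blocking.

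A reader might also infer that a paired test is planned. The bracketed name and the two-group design point to the unpaired test, so this is contradictory naming and does not cause the inflation. Nor can it be said that confidence intervals will be too narrow. Section 5.10.2 plans interquartile ranges and box plots, which are descriptive, and no interval for the between-arm difference.

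The comparison is a secondary endpoint, and a large effect would survive. For 3 against 1 day (SD 21), 34 × 9.88 = 336 per arm at ICC 0.8, still below 363.

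The analysis plan, which is not shown, could add an adjustment. That does not answer the point, because the protocol itself fixes both the test and the sample size. An analysis plan that followed it would carry the mismatch forward.

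**Conclusion.** The mismatch between randomisation and analysis is stated in the protocol and needs no assumption: days are randomised within blocks, while the test and the sample size treat participants as independent. Its size does rest on assumptions. With about 12 tested per day and the correlation lying between days within a block, the type I error is about 0.05–0.06 at ICC 0.01, 0.11–0.12 at 0.05, 0.18 at 0.10 and 0.35 at 0.30. It is lower in the cases described above. The claim of 80% power for 3 against 2 days (SD 21) holds only up to an ICC of about 0.065 with 363 per arm, or 0.14 with 544. The contradictory test name is a separate and smaller error. Both should be corrected before the arms are compared.

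**What to change.** In section 5.10.2, replace the sentence naming the test with wording such as:

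> Arms are compared by a method that respects the randomised screening day and the 2-week block: a permutation test that re-randomises days within blocks, using a rank-based or median statistic. A rank-sum test adjusted for clustering by day is supportive.

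A rank-based or median statistic keeps to the declared median endpoint. It also avoids taking logarithms of same-day results that may be recorded as 0 days. Wherever the between-arm test is named, call it Wilcoxon rank-sum (Mann-Whitney U) and remove the words signed rank.

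In section 5.9.2 and the matching text of the Research Outline, apply a design effect over a stated ICC range and a stated number tested per day. Restate the power claim with the ICC up to which it holds.

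No new data are needed, because the study date and assigned testing strategy are already recorded at enrolment (section 5.8.3). The cost is a p-value that will usually be larger and a less favourable power statement. At an ICC of 0.10, for example, 446 per arm would be needed, which lies inside the expected 363–544. At 0.30 it would be 914, which does not.
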